1. INTRODUCTION

During the first 12 weeks, pregnancy is carried out without significant blood flow from mother to the fetus. Later, fetal circulation in the developing tissues occurs at low oxygen pressure: in fetal blood, rarely pO₂ is higher than 30 mm/Hg. Therefore, from conception to delivery, the development of mammals occurs in hypoxia [1,2]. During delivery, infants are to cope with what could be defined as "*hyperoxic challenge*". The oxidative stress, that is the imbalance between oxidants and antioxidants in favor of the formers, affects tissues by producing free radicals. Extremely low birth weight infants (ELBW, birth weight lower than 1000 grams) are particularly sensitive to the oxidative stress, because of the immaturity of the antioxidant metabolic systems as well as the existence of frequent comorbidities, especially infections that, on their turn, increase the oxidative stress [3]. All the pathologies caused by the oxidative damage are defined as "oxidative stress-related diseases in newborns" [4,5]. These disorders, that are generally developed at the same time by the patient, include bronchopulmonary dysplasia (BPD), retinopathy of prematurity (ROP), necrotizing enterocolitis (NEC), periventricular leukomalacia (PVL) and, at least partially, intraventricular hemorrhage (IVH) [4,5]. EPICure (Extremely Premature Infant Cure) studies carried out in the United Kingdom showed that among premature infants born between the 22nd and the 26th gestational week, and with a postmenstrual age of 26 weeks, 68% of those who survived developed BPD, 21% were affected by ROP at least in one eye and 13% presented serious alterations during brain ultrasound scans [6,7]. Most recent papers described red blood cell transfusions as a main risk factor for the development of these pathologies [8-14] and the overall survival [14-16]. There are various factors explaining the correlation between the number of transfusions and the seriousness of the pathologies due to the oxidative damage, such as the immune modulatory effect (the term "transfusion-related immunomodulation" is used for the transfusion-related immunosuppression syndrome) [17,18] or the inflammation caused by "micro particles" that are released during the storage of red blood cells [19-21]. However, it is increasingly evident the role played by adult hemoglobin (HbA) that, due to its lower affinity to oxygen than fetal hemoglobin, greatly contributes to the oxidative stress [13,22,23]. The harmful role of HbA in preterm has clearly emerged in a recent prospective study, which showed that the incidence of ROP was inversely related to patients' fetal hemoglobin (HbF) levels, with a higher incidence among those showing the lowest levels [13]. In these patients, the level of HbF was obviously inversely proportional to that of HbA [13]. The current neonatal transfusion guidelines, by the Italian Society of Neonatology and the Italian Society of Transfusion Medicine, recommend the use of fresh leukoreduced red cell concentrates and the irradiation of blood components [24].

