Compared to the adult donor blood, cord blood taken from placenta and umbilical vessels has some important characteristics in terms of neonatal transfusions. As a matter of fact, cord red cells contain HbF, which is more physiological than HbA in preterm infants because of its higher affinity to oxygen. Moreover, the immune and infection profile of cord blood is absolutely “naïve”, as shown by the years of experience with hematopoietic transplants [33]. All these characteristics are a valid reason for using it when transfusing preterm infants. The use of autologous or allogeneic umbilical cord blood as an alternative to the transfusion of adult red cells was greatly confirmed by literature to the point that cord blood red cell concentrates were included by the Italian National Blood Center in the blood components acknowledged by the UNI 10529:1996 norm that regulates their traceability (umbilical cord blood red cell concentrates, UCB-RBC, blood component 73). These units can be irradiated like those obtained from adult donors. In a recent study, we tested the ability of the UNICATT Cord Blood Bank to cover the transfusion needs of low birth weight infants who were admitted to the Neonatal Intensive Care Unit (NICU) of our hospital with red cell concentrates from cord blood [46]. The study included patients who were born before the 30th week of gestation and/or with a birth weight lower than 1,500 g and who needed transfusions during the first 28 days of life. After the first transfusion event, each patient was assigned to the treatment arm (umbilical cord blood-packed red cells, UCB-RBC) or to the control arm (adult donor red cell concentrates, A-RBC), depending on the availability of UCB-RBC of the same blood type (ABO-Rh). From March, 1 to February, 28 2014, 20 patients out of the 63 that were hospitalized in the NICU were included in our study. Out of 20 infants, 9 were transfused with UCB-RBC and 11

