with A-RBC. Overall, we transfused 23 UCB-RBC units and 27 A-RBC units. We observed that the two types of blood components led to a similar increase in the hematocrit levels and that the patients that were transfused with UCB-RBC or A-RBC received a similar number of transfusions at similar time intervals. There were no adverse events nor transfusion reactions and no CMV infections were recorded. In this limited number of patients, with an average follow-up of 57 days, the incidence of prematurity-related pathologies appeared to be globally comparable [46]. However, it was interesting to notice that the only two patients who did not develop ROP were only transfused with UCB-RBC [47]. More recently, a prospective study was carried out to show that the incidence of ROP was related to the levels of HbF in patients: the lower the levels, the greater the incidence [13]. Among those patients, the level of HbF was obviously inversely proportional to that of HbA. Therefore, even if it was a limited number of patients, the absence of ROP among the patients who were transfused with umbilical cord blood indirectly confirms the potentially damaging effect of adult blood transfusions [46, 47]. Our feasibility study also demonstrated that with current resources we are able to cover 50% of these patients' transfusion needs [46].

At global level, the implementation of a program for the transfusion of cord blood in a preterm infant could have an important clinical impact. Additionally, the introduction of this transfusion strategy could be an advantage in the rationalization of resources when using blood components. Actually, according to the criteria of cellularity established by the Italian Bone Marrow Donor Registry (IBMDR), less than 10% of cord blood units are cryopreserved and listed for transplants [48].

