3. EXPERIMENTAL DESIGN

3.1 Study design. This study is a prospective non-randomized study to evaluate the correlation between the reduction in the level of HbF (based on the relation between HbF and HbA) before the 36th week of PMA and the type of transfusion (UCB-RBC or A-RBC).

3.2 Duration of the study. The study will have an overall duration of one year. The enrollment of patients will last 10 months. Considering the volume of activity of our NICU and the type of eligible patients, such a period of time was considered adequate to enroll the number of patients necessary to reach the established objectives. As for the transfusions (UCB-RBC or A-RBC), the intervention phase will last from the enrollment to the completion of the 32nd week of PMA, while the weekly monitoring of HbF will continue until the completion of the 36th week of PMA.

3.3 Early study termination. The study will be terminated with the occurrence of adverse events that can be risky for the patients or if the Proposer thinks it is necessary, based on the evaluation of safety data.

3.4 Study termination. The study will be considered over when the collected data make it possible to draw up the final report.

3.5 Study endpoints.

- HbF levels before and after each transfusion;
- Average HbF levels (at 32 weeks of PMA; at last control)
- Prevalence of ROP and/or BPD and/or NEC and whatever health problems (infectious pathologies, hemorrhages including IVH, kidney failure, thromboembolism, surgical complications, etc.) before the 36th week of PMA;
- Transfusion efficacy of UCB-RBC compared to A-RBC (all transfusions before the 36th week of PMA, evaluated based on a) average time interval between two subsequent transfusions and b) average increase in the post-transfusion capillary hematocrit (Δ Hct).

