5.4 The collection of cord blood will be carried out in the birth centers that are part of the Cord Blood Bank, according to the procedures used by the Bank itself. The collected units will be adequately conserved at low temperatures (2-6°C) and fractionated within 24 hours. The units that are not eligible for transplant because of low cellularity (total nucleated cells <1,200 x 10⁶), with a volume >60 ml excluding the anticoagulant (CPD, Citrate, Phosphate, Dextrose), without clots and/or hemolysis, will be considered eligible for fractionation to obtain UCB-RBC. Eligible UCB units will be fractionated by an automatic blood component processing system (the UNICATT Cord Blood bankl will use Compomat[®] G4 by Fresenius HemoCare GmbH, D-61346, Bad Homburg, Germany). Red cell concentrates will be resuspended in a preservative solution containing adenosine, glucose and mannitol (SAGM, ratio red cell: SAGM = 2:1) and filtered with the filter Purecell[®] NEO Neonatal High Efficiency Leukocyte Reduction Filter (Pall, East Hills, NY, USA) to remove leukocytes. Blood cultures for bacteria and fungi will be set up. Only the units that tested microbiologically negative will be considered eligible for transfusion (blood cultures, molecular and serological tests for HCV, HBV, HIV and syphilis). UCB-RBC units will be stored at a temperature of 2-6°C for 14 days, in order to allow the γ -irradiation (¹³⁷Cs) when they are assigned to the patient.

5.5 Transfusion request. Units will be requested according to the procedures established by the Blood Transfusion Service, based on the current legislation and in accordance with the guidelines reported in Annex III. When a blood request arrives, the hematologist on duty at the Blood Transfusion Service will check if the patient's name is included among those enrolled in the study and the date of completion of the 32nd week of PMA; then he/ she will identify ABO-Rh(D) units to transfuse (UCB-RBC if available, otherwise A-RBC). The transfusion dose will be determined regardless of the type of blood component being used and will be established according to the criteria generally implemented in the NICU. The UCB-

RBC and A-RBC units will be transfused within six hours in order to reduce functional alterations of red cells and the risk of microbial contamination.

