6.3 Statistical data analysis. The continuous variables will be expressed as mean (\pm SD) or as median (interquartile ranges, IQR); all deviations from normality will be detected with the Shapiro-Wilk test. The categorical variables will be expressed as n, (%), percentage). HbF levels in different type of transfusions will be compared in univariate analysis Mann-Whitney U test, end Kruskall Wallis test). Similarly, the transfusion efficacy analysis will be carried out based on a UCB-RBC and A-RBC non-inferiority study design by comparing the average time interval between two subsequent transfusions and the average post-transfusion capillary Ht

increase (Δ Ht) (Mann-Whitney U Test). The transfusion sample included in the study makes it possible to detect a difference between groups that is equal to at least 1 standard deviation with type I error $\alpha = 0.05$ and type II error $\beta = 0.2$ and a medium effect size (0.6). The correlation between the type of transfusion and other variables (prematurity related pathologies) will be tested using Fisher's exact test. Secondarily, in order to evaluate the effect of HbF reduction on the onset of prematurity-related pathologies, the levels of HbF levels will be inserted in a multiple linear regression model, by expressing the correlation between the onset of prematurity-related pathologies and the variables in terms of odds ratios (ORs \pm 90% confidence interval).

6.4 The primary outcome analysis will be tested on "E", "T" and "PP" sets. Transfusion efficacy outcome will be tested on "T" and "PP" sets.

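### Product is re-chosen at every request, so the Fisher tests of disease by type of transfusion are confounded with the number of transfusions, in a direction set by a grouping that section 6.3 leaves undefined

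*Combined protocol and SAP*

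**What the plan says.** - Section 3.1: "This study is a prospective non-randomized study". Nothing assigns an infant to a product for the whole study.
- Section 5.5: "When a blood request arrives, the hematologist on duty at the Blood Transfusion Service will check if the patient's name is included" on the list of enrolled infants, and will then "identify ABO-Rh(D) units to transfuse (UCB-RBC if available, otherwise A-RBC"). The choice is made afresh at each request.
- Section 6.2 expects about four transfusions per infant with the two products in a 1:1 ratio, and quotes 3 ± 1.7 per infant from the sponsor's earlier study. The Introduction puts UCB-RBC coverage of transfusion needs at 50%.
- Section 6.3: "The correlation between the type of transfusion and other variables (prematurity related pathologies) will be tested using" Fisher's exact test. The unit of analysis, the class of an infant given both products, and any adjustment are not stated. The regression that follows concerns HbF level, not product, and lists no covariates. Section 6.4 assigns analysis sets to the primary and transfusion-efficacy outcomes but not to these tests.
- Introduction: "Most recent papers described red blood cell transfusions as a main risk factor for the development of these pathologies". It goes on to refer to a correlation between the number of transfusions and the seriousness of disease.
- Section 5.9 already records the date, number, type and volume of transfusions.

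**The concern.** An infant who needs one transfusion always ends up on a single product. An infant who needs six will almost certainly receive both. Classing infants by what they actually received therefore partly sorts them by how many transfusions they needed. By the protocol's own account, that number goes with ROP, BPD, NEC and IVH. An unadjusted comparison then mixes any product effect with transfusion need.

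Because the grouping is not fixed, it can be chosen after the data are seen, and that choice can decide which product looks better. One such reading already appears in the Introduction, which notes of the earlier study that "the only two patients who did not develop ROP were only transfused with UCB-RBC" and takes this as indirect support for harm from adult blood.

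**Working it through.** **The plan's own figures.** 25 infants × 8 weeks − 1.9 deaths/month × 2 months = 196.2 weekly HbF measurements. Half of that is 98.1 transfusions. Both match the stated 196 and 98, and 98/25 ≈ 3.9 transfusions per infant.

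**Inputs from the documents.** 25 infants; 3 ± 1.7 or about 4 transfusions each; UCB-RBC probability p = 0.5 per transfusion (1:1 ratio, 50% coverage).

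**Assumptions.** Requests are independent. Odds of disease are multiplied by 1.3, 1.5 or 2.0 per transfusion, with overall risk 30% or 50%; the documents give only the direction of this link. Product has no effect.

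**Step 1: chance of staying on UCB-RBC.** P(UCB-only | n) = 0.5^n, that is 50%, 25%, 12.5%, 6.25% and 1.6% for n = 1, 2, 3, 4 and 6. At n = 4, P(both products) = 1 − 2 × 0.0625 = 87.5%.

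**Step 2: who is in each group.** Counts n = 1 to 12 are weighted by a normal density centred on 3 or 4 with SD 1.7. The UCB-only share is Σ wₙ 0.5^n.

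| Centre | UCB-only infants of 25 | Mean transfusions, UCB-only | Mean transfusions, any A-RBC |
|---|---|---|---|
| 3 | 4.1 | 2.1 | 3.5 |
| 4 | 2.6 | 2.6 | 4.3 |

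Infants given both products number about 17 to 20 and average 3.8 to 4.5 transfusions.

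**Step 3: odds ratio with no product effect.** Disease risk is logistic in n, calibrated to the overall risk and averaged within groups.
- Any A-RBC against UCB-only: 1.44 to 2.53 (centre 3) and 1.54 to 2.88 (centre 4). UCB-RBC looks protective.
- Any UCB-RBC against A-only: the same values by symmetry at p = 0.5, now against UCB-RBC.
- UCB-only against A-only: 1.0 at p = 0.5, because both groups have the same distribution of n. At p = 0.3, with a zero-truncated Poisson count of mean 4, the group means would be about 1.7 (UCB-only) and 2.9 (A-only), and this comparison would also favour UCB-RBC.

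**Step 4: simulation of 20,000 trials of 25 infants.** This used other count distributions (zero-truncated Poisson, mean 4; shifted negative binomial, 3 ± 1.7), odds ratios of 1.25, 1.5 and 2.0 per transfusion, and 50% overall risk.
- UCB-only against any A-RBC: 0.64, 0.48, 0.32 (mean 4) and 0.72, 0.57, 0.42 (mean 3). For the last, risks of 0.333 and 0.543 give (0.333/0.667)/(0.543/0.457) = 0.42.
- UCB-RBC looked better in 62 to 81% of trials.
- Two-sided Fisher at 0.05 rejected in the protective direction in 1.5 to 6.6% of trials, against 0.6 to 1.0% when transfusion number had no effect on disease. At 20% overall risk the rate was under 0.2%.
- With availability correlated within infants (0.3), the odds ratio moved to between 0.56 and 0.71.

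**Step 5: grouping by first product.** The odds ratio was 0.99 to 1.01 in every scenario, with protective rejections in 1.0 to 2.2% of trials. The contrast is small. Given n, expected UCB-RBC units are 1 + 0.5(n − 1) against 0.5(n − 1), a difference of one unit; for n = 4, 2.5 against 1.5. The mean difference in UCB-RBC share is E(1/n), about 0.41 (centre 3) or 0.31 (centre 4).

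**The case against.** **The bias belongs to a grouping that the plan does not state.** This stands, and it shapes the point. A reader might infer that the Fisher test will show UCB-RBC as protective. The documents do not support that: section 6.3 fixes no grouping, and the direction can reverse or vanish with the choice made.

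**The test will rarely mislead.** This also stands. With 3 to 5 UCB-only infants, Fisher's test is conservative and the usual result is non-significance. The problem lies in the estimate.

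**Independence across requests is assumed.** The 50% figure is coverage of patients' needs, not a probability per request. Units are matched on ABO-Rh(D), so availability can cluster within infants. Clustering shrinks the bias but does not remove it.

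**These are not listed outcomes.** Section 2 lists HbF against comorbidities, not product against disease, and section 10 leaves the impact of blood components to later randomized studies. This lowers the importance. Nor do the documents say that a protective Fisher result is what the sponsor means to carry forward. Even so, the tests are planned in 6.3 and disease prevalence is an endpoint in 3.5.

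**The earlier study.** A reader might infer that it avoided the problem, since "After the first transfusion event, each patient was assigned to the treatment arm" or to the control arm according to availability. That sentence does not say that infants then stayed on one product, so it cannot be used as evidence either way.

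**Conclusion.** The concern holds as a gap in the analysis plan that should be closed. Followed as written, section 6.3 permits several groupings by product received, and most of them are confounded with transfusion number. With no product effect, the size is an odds ratio of about 1.4 to 2.9, towards UCB-RBC under one grouping and against it under the opposite one. UCB-only against A-only is unbiased only near 50% availability.

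These sizes rest on assumed odds ratios of 1.3 to 2.0 per transfusion, overall risks of 30 to 50%, and independent availability of 50%. The direction of the link between transfusions and disease is the protocol's own. False significance in the protective direction is at most about 7% in the scenarios run. The main harm is a biased estimate whose sign depends on a choice not yet made.

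**What to change.** Change section 6.3 to:

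1. State that the infant is the unit of analysis, and define the group for the Fisher tests as the product issued at the first transfusion after enrollment. Name the analysis set; this grouping requires transfused infants.
2. Add a supporting logistic model, penalised or exact given 25 infants, of disease on the UCB-RBC share of transfusions. Adjust for their total number, and for gestational age if numbers allow. Count transfusions up to one common PMA cut-off for all infants. Counting only up to diagnosis would give affected infants shorter exposure windows than infants never diagnosed.
3. Label any comparison by product actually received as descriptive, with no product conclusion drawn.

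The cost is wording only. Section 5.9 already collects the data, and no clinical procedure changes. There are two downsides to state in the plan. First-product groups differ by only about one UCB-RBC unit per infant on average, so the contrast is diluted. The approach also assumes that availability at the first request is unrelated to the infant's risk.

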2. OBJECTIVES OF THE STUDY

The objective of the study is to investigate the correlation between the levels of HbF and the use of umbilical cord blood red cell concentrate transfusions in ELBW preterm infants and/or infants who were born before the 30th week of gestational age (GA). Since transfusions are one of the main mechanisms to reduce HbF, they will be carried out with umbilical cord blood red cell concentrates (UCB-RBC). Our objective is to demonstrate that UCB-RBC transfusions, until the 32nd week of PMA, guarantee average levels of HbF that are higher than in adult-RBC (A-RBC) transfusions. The following outcomes were defined:

Primary outcome:

- Average levels of HbF at 32nd week of PMA in patients receiving different transfusion support.

Secondary outcomes:

- To show that UCB-RBC transfusions are not less effective than A-RBC transfusions, as for the post-transfusion increase in the hematocrit and the interval between two transfusions.
- To show the association between average levels of HbF during the inpatient stay and comorbidities (ROP, BPD, NEC, PVL and IVH) or deaths occurred within 36 weeks of PMA.

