6. STATISTICAL CONSIDERATIONS

6.1 Definition of analysis sets

- **Enrolled (E) set or Intent-to-treat (ITT) analysis.** It will comprise all the enrolled patients, regardless of the administration or not of RBC transfusions.
- **Treated (T) set.** This group will comprise all the patients who were at least administered one transfusion, regardless of the completion of the observation period (36th week of PMA). Excluded from this set are the enrolled patients who were not transfused.
- **Per-Protocol (PP) set.** This group will comprise all the transfused patients who completed the observation period (36th week of PMA) or who died after completing it.

6.2 Calculation of sample size. The main goal of the study is to correlate the average HbF levels to the type of transfusion (UCB-RBC or A-RBC). With a population of 25 patients that will be studied during the following 8 weeks and a mortality rate of 1.9 patients/month, we expect to have 196 weekly doses of HbF to correlate to 98 transfusions. The total expected number of transfusion from birth to the completion of the 36th week of PMA was calculated to be around four transfusions per patient, with an UCB-RBC:A-RBC ratio of 1:1. In fact, for those patients with birth-determined characteristics similar to those of the studied population, the average number of transfusions within the 36th week of PMA is around 4 transfusions/patient [25], while in our previous study the average number of transfusions was 3 ± 1.7 [46]. In accordance with the literary data, preterm infants have an expected HbF concentration between 85% and 90% at birth and between 70% and 75% at the 36th week of PMA [54]. We expect that for the newborns who will not be transfused the HbF levels will stay in this range (70%-90%), while for the patients who will be transfused with adult red cells, HbA will dilute HbF. Even though there are no literary data yet, if we know the volume of transfused red cells (20 ml/kg) and the patient's blood volume, we can also assume that, for every adult red cell transfusion, HbF will be reduced by 15-20% compared to the pre-transfusion values until reaching levels lower than 20% among those patients who were transfused more than 4 times with adult blood.

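### Section 6.3 reports odds ratios from a linear model of disease onset, and no HbF summary in the plan stops at diagnosis, so adult transfusions given after diagnosis can make low HbF look harmful.

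*Combined protocol and SAP*

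**What the plan says.** - **Model (section 6.3).** To evaluate the effect of HbF reduction on disease onset, HbF levels "will be inserted in a multiple linear regression model, by expressing the correlation between the onset of prematurity-related pathologies". The effect measure is to be the odds ratio, with 90% confidence intervals. The section does not say which HbF summary enters the model, or over what period.
- **Exposure (section 2, second secondary outcome).** The association of interest is between "average levels of HbF during the inpatient stay and comorbidities (ROP, BPD, NEC, PVL and IVH) or deaths occurred within 36 weeks of PMA".
- **Other HbF summaries (section 3.5).** "Average HbF levels (at 32 weeks of PMA; at last control".
- **Follow-up (section 3.2).** "the weekly monitoring of HbF will continue until the completion of the 36th week of PMA".
- **Which unit is issued (section 5.5).** "UCB-RBC if available, otherwise A-RBC".
- **Expected use and dilution (section 6.2).** The plan expects "around four transfusions per patient, with an UCB-RBC:A-RBC ratio of 1:1". For each adult transfusion, "HbF will be reduced by 15-20% compared to the pre-transfusion values".
- **Diagnoses (sections 5.8 and 5.9).** Section 5.8 defines ROP, BPD, NEC and IVH, and places the BPD diagnosis at 36 weeks PMA. PVL is an outcome only in section 2. The data items listed in section 5.9 include transfusion dates but no date of diagnosis.

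**The concern.** There are two separate faults.

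First, the named model and the named effect measure do not belong together, so the sentence cannot be carried out as written.

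Second, the stated aim is an effect on onset, which requires HbF measured before onset. A mean over the whole stay also contains HbF measured after it. If an infant is diagnosed with NEC, for example, and then receives an adult unit, the mean falls because of what followed the disease. The model would read that fall as a cause of the disease. The error runs in the direction the study expects, and section 10 presents the study as a possible basis for randomized trials on whether harm follows from HbF reduction.

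**Working it through.** The plan states no expected odds ratio, event count or power for this model, so there is no figure of its own to reproduce.

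**1. Can the linear model be converted?** The slope of a linear model for a 0/1 outcome is a risk difference. With a true odds ratio of 2 per SD and intercept risks of 20%, 40% and 68%, the simulated linear slopes are 0.109, 0.151 and 0.142. Exponentiated, they give 1.12, 1.16 and 1.15. Exponentiating therefore does not recover the odds ratio.

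**2. Does any HbF summary stop at diagnosis?**

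| Summary | Section | Can include HbF after diagnosis? |
|---|---|---|
| Average over inpatient stay | 2 | Yes |
| At 32 weeks PMA | 2, 3.5 | Yes, for diagnoses before 32 weeks |
| At last control | 3.5 | Yes |

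BPD is diagnosed when HbF monitoring ends, so little HbF can follow it.

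**3. How far does one later adult unit move the mean?** From section 6.2: HbF of 85-90% at birth and 70-75% at 36 weeks PMA, an 8-week study period, and a 15-20% relative fall per adult unit. Assumed: a straight line between midpoints, HbF(t) = 87.5 - (15/8)t, and two adult units (half of four) at weeks 1 and 3. With f = 0.85 or 0.80, a further unit at week s lowers the 8-week mean by

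(1 - f) × f² × [87.5(8 - s) - (15/8)(64 - s²)/2] / 8.

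- s = 4: the bracket is 350 - 45 = 305. Fall = 0.15 × 0.7225 × 305/8 = 4.1 points, or 0.20 × 0.64 × 305/8 = 4.9 points.
- s = 6: the bracket is 175 - 26.25 = 148.75. Fall = 2.0 or 2.4 points.

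**4. What does that do to an odds ratio when HbF has no effect?** Simulation with 25 infants over 8 weeks and the HbF line and dilution above. All other inputs are assumed:
- baseline HbF SD 2.5
- weekly adult-transfusion probability 0.25 (mean two per infant)
- event hazard 5% per week, independent of HbF (about 34% of infants affected)
- one extra adult unit in the week after the event for none, half or all cases
- Firth logistic regression with gestational age, in runs with at least two events

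Median odds ratio per 10 points lower HbF (true value 1); ranges cover independently coded runs:

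| | None | Half | All |
|---|---|---|---|
| Whole-stay mean | 1.0 | 1.3-1.4 | 1.7-1.8 |
| 90% interval excludes 1 | 5-6% | 8-10% | 19-21% |
| Value at week 4 (32 weeks PMA if born at 28) | 1.01 | 1.21 | 1.45 |
| Value at week 8 (last control) | 1.01 | 1.32 | 1.77 |

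Varying hazard, transfusion probability and SD moved the whole-stay result to 1.3-1.5 (half) and 1.7-2.2 (all).

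A second simulation used a different structure: 40% diseased, diagnosis on days 7-42, and an average of 0, 1 or 2 extra adult units per case spread over the remaining days. The whole-stay mean gave 0.99-1.02, 1.28-1.41 and 1.62-1.91. The value at 32 weeks was less affected: 1.10-1.14 with one extra unit.

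**5. Do the remedies work under the same null?** A pooled weekly model gave 1.00-1.02 and a two-week landmark mean 1.02-1.09. HbF averaged to the diagnosis day, with disease-free infants cut at a matched index day, gave 0.98-1.02. Cutting at diagnosis in cases only gave 0.22-0.46 across both simulations: the bias reverses, because cases are then averaged over earlier, higher-HbF weeks.

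**The case against.** **Linear is probably a slip for logistic.** That is plausible, and the correction is then one word. It is still needed.

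**Section 6.3 does not commit to the whole-stay mean, and its aim is compatible with HbF measured before onset.** This is fair. What is certain is that the exposure is unspecified. But the only exposure given for this objective, in section 2, is the inpatient-stay average, and no lagged, landmark or time-updated analysis appears anywhere.

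**The size is assumed.** This stands. Bias requires diagnosed infants to receive more adult units after diagnosis than other infants do, and the documents do not say whether they will. If none do, there is no bias. Cord units are issued first when available, so not every extra unit would be adult. If every case received one extra unit at the planned 1:1 mix, the half column would apply. That mix may not hold after 32 weeks PMA, when the intervention phase ends.

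**Death.** Section 2 lists death, so a reader might infer that early deaths, with shorter and higher-HbF windows, also distort the result. The documents do not support making that a defect: section 6.3 does not model death, and the expected number is unclear. Nor does the planned total of 196 doses settle how to read the mortality figure. Taken literally, 25 × 8 - 1.9 × 2 = 196.2; taken as 1.9%, 200 × 0.981 = 196.2.

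**Conclusion.** The point holds and should be fixed, as a modest change to a secondary analysis. The mismatch between model and effect measure, and the absence of any HbF window ending at diagnosis, are plain on the text. The bias is a possibility whose direction follows from the plan's own dilution figure. Its size is not known: the odds ratios and false-positive rates above are illustrations that rest on an assumed rate of extra adult transfusions after diagnosis, together with assumed event timing and HbF spread.

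The point applies to ROP, NEC and IVH, and to PVL if it is modelled as section 2 implies. A reader might infer that the BPD analysis or the primary HbF comparison is also compromised. The documents do not support that: BPD is diagnosed at the end of HbF monitoring, and the primary comparison is of HbF by transfusion type and does not use this model.

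**What to change.** - In section 6.3, replace linear with logistic regression and label the analysis exploratory. A penalised fit such as Firth's is sensible because events will be few.
- For ROP, NEC, IVH and PVL, use only HbF measured before diagnosis, over a window common to infants with and without the event. Choose one form in advance: a landmark mean with earlier events excluded, or a pooled weekly model with a PMA-week term.
- State that HbF will not be cut at diagnosis in cases only.
- Align the section 2 objective with the chosen window, and say whether PVL is modelled.
- Record the date of first diagnosis. Section 5.9 does not list it; the case report form itself is not in the documents.

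**Cost.** Text in sections 2 and 6.3 and one date field. No extra blood is needed, since HbF is already planned at least weekly. Early events, especially IVH, will contribute little prior HbF. The landmark form is conservative (false positives of 0.7-1.1% at a nominal 5%), and intervals will be wide with 25 infants. The change does not address transfusions given for illness that is developing but not yet diagnosed, so it should not be presented as removing all reverse causation.
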